### **Patient and public involvement**

The intervention, study design, and research questions were developed with adolescents with ADHD in mind as the researchers have extensive (clinical) experience with ADHD. To fine-tune and adapt SIESTA and the study design to the needs and perceptions of adolescents with ADHD and their parents, a pilot study (N=8) preceded the RCT.[33] Adolescents with ADHD and sleep problems and their parents who received the pilot version of SIESTA gave feedback on the intervention and addressed points of improvement in focus groups. Focus groups were conducted separately with adolescents and parents. Regarding the intervention, feedback was given on the duration, complexity, feasibility, suitability, relevance and representation of ADHD in the materials used in treatment. Regarding the study design and assessment protocol, feedback was given on the (amount of) questionnaires, usability and feasibility of the sleep diary, and actigraphy.

### **Randomization and blinding**

Participants are randomly assigned to either the treatment (SIESTA+TAU) or control (TAU) group with a 1:1 allocation stratified by ADHD medication use (yes/no) and location (Leuven, Antwerp, Hasselt, Brussels, Gent, Roeselare) using permuted blocks of random sizes.[34,35] We randomize per location to ensure practical feasibility for our therapists of the KU Leuven (i.e. there is a maximum amount of adolescents that can be treated per location). Randomization is done by an

independent researcher who is not involved in the study in any way. Due to the nature of the psychological treatment neither participants nor clinicians can be blinded to allocation. Researchers who are responsible for the practical side of the study (LK, FM), are not blinded to allocation, however, the principal investigator ([name]) and the other researchers DB, BB and MD are blinded throughout the study.

### **Intervention and comparison**

SIESTA is based on a CBT sleep intervention for typically developing adolescents and a CBT intervention focused on motivational planning for adolescents with ADHD, both developed by (amongst others) the project applicants.[36,37] The training follows a structured workbook for the adolescent which can be used during sessions and at home.[24] The instructions for the therapist are described in a therapist manual.[25] SIESTA consists of seven individual sessions with the adolescents, and two parental sessions. An overview of the content of the sessions can be found in Table 2. This RCT uses as control condition TAU for ADHD symptomatology. In Flanders TAU for ADHD primarily consists of medication with stimulants.

**Table 2**

*Overview of the Adolescent and Parent Sessions of SIESTA*

Session 1	Psychoeducation on sleep in adolescents with ADHD. Focus on goal setting and adolescent motivation.
Session 2	In-depth psychoeducation on sleep hygiene (sleep practices, physiological factors like caffeine and alcohol use, sleep environment). Adolescent sleep behavior research: What does the adolescent already know and what more information is needed?
Session 3	Adjustments to align better with healthy sleep practices. Discussing trying out an alarm and relaxation exercises.
Parent session 1	Psychoeducation on sleep in adolescents with ADHD. Discussing and creating realistic expectations of parents towards the intervention and their adolescent.
Session 4	Aimed at drawing up a functional and topographical analysis of the sleep problem and specify the goals of session 1 based on that. An individualized sleep plan is made to target their sleep problem.
Session 5	An extra plan can be added to the sleep plan: this can focus on rumination, planning and organization, circadian rhythm and motivation.
Session 6	The sleep plan is finalized. Making sure it is adapted towards the adolescent.
Parent session 2	Finding a balance between controlling and letting go of the sleep of the adolescent. Positive communication about the sleep of the adolescent.
Session 7	Relapse prevention.

### **Outcome measures**

#### **Primary outcomes**

**Objective sleep architecture: TST, SOL, SE, and NoA.** Sleep is registered with wrist actigraphy (Motionwatch, CamNtech Ltd) as objective measurement. Participants wear an actigraph for five school nights and two weekend nights, as based on previous research,[38] this is sufficient to be able to compute reliable sleep architecture estimates. Actigraphy has been reliably used in adolescents with sleep problems and has been shown to be sensitive to treatment effects.[13,38,39] Participants use the event marker button on the actigraph to indicate lights out and getup times.[40] If they forget to press the button, those time points are extracted from the sleep diary data. Using this data, TST (time asleep between sleep onset and sleep offset), SOL (time from lights out to sleep onset), and SE (percentage of time spent asleep TST while in bed TiB), and NoA (number of times awake after sleep onset and before sleep offset) are calculated.

**Subjective sleep architecture.** Sleep is registered with a sleep diary as subjective measurement. The adolescents fill out the sleep diary for five school nights and two weekend nights, keeping track of lights out, sleep onset, sleep offset and getup via an ecological momentary assessment app m-Path.[41] TST, SOL, SE, and NoA are calculated analogous to the actigraph data.

**Sleep problems.** Sleep problems are measured using two self-report and one parent-reported questionnaire. The following two subscales of the School Sleep Habits Survey are used: Sleepiness and sleep/wake problem behaviors.[42] This is a validated self-report questionnaire with acceptable internal consistency (sleepiness;  $\alpha = .70$ ; sleep/wake problem behaviors;  $\alpha = .75$ ).[43] To measure sleep deprivation, the Chronic Sleep Reduction Questionnaire is used (CSRQ).[44] This self-report questionnaire is validated, and has good internal consistency ( $\alpha = .85$  in clinical and  $\alpha = .87$  in control sample).[45] Children Sleep Habits Questionnaire (CSHQ) is used to gain insight in parents' perception of their children's sleep.[46] This is a validated, parent-report questionnaire with acceptable internal consistency ( $\alpha = .78$  in clinical and  $\alpha = .68$  in control sample) and acceptable test-retest reliability (.62 - .79).[46]

**Sleep hygiene.** Sleep hygiene is measured with the revised Adolescent Sleep Hygiene Scale (ASHSr).[47] This is a validated self-report questionnaire with adequate to good internal consistency (total scale  $\alpha = .84$  and subscales  $\alpha = .60 - .81$ ).[47]

### **Secondary outcomes**

**ADHD symptoms.** Inattention and hyperactivity-impulsivity subscales of the Disruptive Behavior Disorder Rating Scale (DBDRS) are used to measure ADHD symptoms.[48] This parent-reported questionnaire is validated, and the internal consistency of the scales in a Flemish sample is good for inattention and hyperactivity-impulsivity.[48]

**Comorbidities.** Symptoms of multiple comorbidities are measured using self-, parent- and teacher-report questionnaires. The ODD subscale of the parent-reported DBDRS is used.[48] To evaluate symptoms of anxiety, the SCARED-R is administered.[49] The SCARED-R is a validated, self-report questionnaire with good psychometric properties.[50] The self-reported Child Depression Inventory 2 (CDI-2) is administered to assess depressive symptoms.[51] Again, this is a validated questionnaire with good internal consistency ( $\alpha = .88$ ).[51]

**Functional outcomes.** Parent-adolescent conflict is measured using the Conflict Behavior Questionnaire (CBQ).[52] This is a validated, parent-report questionnaire with acceptable to good internal consistency (appraisal of parent;  $\alpha = .73$ ; appraisal of dyad;  $\alpha = .89$ ).[53] To evaluate adolescents' educational achievement, parents complete the Homework Problems Checklist (HPC)[54] and teachers the Classroom Performance Scale (CPS).[55] Both questionnaires are validated and have an excellent internal consistency (HPC:  $\alpha$  ranging from .90 to .92; CPS: academic competence;  $\alpha = .98$ ; interpersonal competence;  $\alpha = .91$ ).

Additionally, exploratory at baseline two questionnaires are assessed as potential moderators; the self-rated Quick Delay Questionnaire (QDQ [58]) and the parent/guardian views on neuropsychological (dys)functioning of their adolescents (the Cognition And Motivation in Everyday Life; CAMEL [59]).

### **Sample size estimates**

A recent study in typically developing adolescents with sleep problems found large effects ( $\beta = 0.91$ ) at post-test of a CBT sleep treatment as compared to waitlist controls on their primary sleep related outcome measure (objectively measured) and a medium effect size for reduction of ADHD symptoms[13,14]. Based on this research, moderate to large effect sizes can be expected for SIESTA in combination with TAU for ADHD on sleep outcomes as compared to TAU for ADHD only. Therefore, using G\*power we calculated with this large effect size a power of .8 and an alpha of .5 for our desired sample size. There are at least 40 participants per condition needed for analyzing the data implementing a linear mixed effects model. However, to anticipate for possible drop-out or lack of response on assessment (although expected to be minimal due to inclusion of motivational interviewing and the pilot study) and as the effect size of the ADHD outcome is medium and not large

[d=.55] an additional 15% will be recruited. Resulting in a total of 92 participants, with 46 participants per condition.

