#### **Participant recruitment**

Participants with ADHD and sleep problems are recruited through the ADHD clinic of the UZ Leuven (Child and adolescent psychiatry services UZ Leuven), PraxisP (the academic clinical centre of the Faculty of Psychology and Educational Sciences, KU Leuven) and the network of the advisory committee (ZitStil, VvGT, Ligant, CARs, Sig vzw, BASS). For the RCT, 92 to 100 adolescents and their parent(s)/guardian(s) will participate in the study. Only minors are recruited for the study (going to school and aged 13-17).

At the start of a diagnostic trajectory of the ADHD clinic, parent(s)/guardian(s)/guardians of the child are asked whether they could be contacted in the future for participation in clinical studies and information will be given about the current study.

Further, participants can specifically apply for the purpose of this study to the ADHD clinic. There are different possibilities to contact the researchers when participants are interested; e-mail addresses,

phone numbers and QR code (to website).

GDPR will be applied as the adolescents receive an explanation conform their development level prior to their participation in the study and the participants parent(s)/guardian(s) must always give permission to participate in the study. Adolescents are asked assent to participate in the study, and if they do not agree, they cannot participate. Even with the assent of the adolescent, consent from the parent or guardian for participation is still required. Parent(s)/guardian(s) will sign an informed consent document. In the informed consent form, permission to participate, consult the patient files and collect data are asked. Both the informed consent and assent will be discussed in detail with the participants in understandable language. Adolescents and their parent(s)/guardians(s) are told that they can follow this treatment at no cost and that they receive a reasonable compensation.

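### The sample-size paragraph cannot be reproduced from its own inputs: alpha is printed as .5, 40 per condition does not follow from an effect of 0.91, and the single 15% add-on is not shown to provide for the d = .55 ADHD outcome

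*Combined protocol and SAP*

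**What the plan says.** All of the following is in the Combined protocol and SAP.

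- **Sample size estimates** takes a large effect (β = 0.91) on an objective sleep measure from a trial of CBT against waitlist in typically developing adolescents. It continues: "we calculated with this large effect size a power of .8 and an alpha of .5 for our desired sample size".
- It concludes: "There are at least 40 participants per condition needed for analyzing the data implementing a linear mixed effects model".
- One add-on then serves two purposes. The first is "to anticipate for possible drop-out or lack of response on assessment". The second is that the ADHD effect is only medium: "d=.55] an additional 15% will be recruited". The result is 46 per condition, 92 in all.
- **Randomization and blinding** gives 1:1 allocation.
- **Secondary outcomes** lists ADHD symptoms, so the d = .55 outcome is not primary.
- **Statistical analysis** plans a mixed model over three time points and an unspecified correction for multiple testing. It standardises effects by the pooled SD of change scores.

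The number of tails, the expected drop-out rate, the within-person correlation, the scale of β and the G*Power test family are not stated.

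**The concern.** The printed alpha is the only significance level in the documents, and it is not one that a trial would use. Replacing it with .05 does not bring back 40 per condition from an effect of 0.91, so a second figure must also be wrong or come from inputs that are not shown.

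The third problem affects interpretation. The paragraph tells the reader that a 15% increase makes room for an effect little more than half the size of the planning effect, and for drop-out as well. Required numbers grow with the inverse square of the effect, so 15% is far too small a step for that. At stake are whether the sample-size justification can be checked at all, and how a null result on ADHD symptoms would be read if the plan says that outcome was provided for.

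**Working it through.** **Inputs.** From Sample size estimates: effects 0.91 and .55, power .80, alpha .5 as printed, 40 and then 46 per condition, add-on 15%. From Randomization and blinding: 1:1. Assumed: 0.91 and .55 are standardised mean differences; alpha .05 was intended; two-sample t-test, two-sided unless noted. Per-arm formula (normal approximation): n = 2(z_alpha + z_power)² / d². Final figures use the noncentral t.

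**1. The plan's own step.** 40 × 1.15 = 46 and 2 × 46 = 92. This reproduces.

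**2. Alpha as printed.** n = 2(0.674 + 0.842)² / 0.91² = 5.6, so about 6 per arm.

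**3. Alpha .05, effect 0.91.** n = 2(1.960 + 0.842)² / 0.91² = 19.0. The noncentral t gives 19.96, so 20 per arm, or 40 in total (power 80.1%). Other readings:
- one-sided .05: 16 per arm
- d = 0.80 in place of 0.91: 26 per arm
- repeated-measures F-tests with f = 0.91/2 = 0.455, two or three time points and correlations from 0 to .7: 8 to 50 in total

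None gives about 80 in total.

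**4. What 40 per arm delivers.** Power is 98% for 0.91. The effect detectable with 80% power is about 0.63.

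**5. The add-on, on the plan's own premise.** In any fixed design n is proportional to 1/d². Moving from 0.91 to .55 multiplies n by (0.91/0.55)² = 2.74. If 40 were needed for 0.91, then .55 would need 40 × 2.74 = 109.5, so about 110 per arm. Conversely, 15% more participants move the detectable effect only from 0.91 to 0.91/√1.15 = 0.85, with nothing left for drop-out. This step needs no choice of test.

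**6. The add-on, calculated directly.** For d = .55, n = 2(1.960 + 0.842)² / 0.55² = 51.9. The noncentral t gives 52.9, so 53 per arm. No drop-out rate is stated, so two losses are shown as assumptions: 6/46 = 13% leaves 40, and 46 × 0.85 = 39.1 leaves 39.

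| Analysed per arm | Power at .55, two-sided .05 | Power at .55, one-sided .05 | Detectable d, two-sided .05 |
|---|---|---|---|
| 46 | 74% | 83% | 0.59 |
| 40 | 68% | 79% | 0.63 |
| 39 | 67% | 78% | 0.64 |

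**7. Sensitivity to what is not stated.**
- *Baseline adjustment, d on the raw-score scale:* n is multiplied by 1 − ρ². With an assumed pre-post correlation of .5, 51.9 × 0.75 = 38.9, so 39 to 40 per arm. With .3, 51.9 × 0.91 = 47.2, so about 48.
- *d already on the change-score scale used in Statistical analysis:* that gain is already included and does not apply again.
- *Multiplicity:* with two-sided alpha .025 (two Bonferroni tests, for illustration), power at .55 with 46 per arm is 64% and the detectable d is 0.65.

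**The case against.** The strongest reply is that the power figures for .55 rest on a test the plan does not name. The plan announces a mixed model, and baseline information or a one-sided test could bring .55 to about 80% power with 40 to 46 per arm. One repeated-measures variant does give 80 in total: a between-group test on two measurements with correlation .5, where n is multiplied by (1 + .5)/2 = 0.75 and 53 × 0.75 = 39.7. But it does so for .55, whereas the plan attributes the 40 to the large effect and then adds 15% because the ADHD effect is smaller. So this stands as a reason to say not shown to cover, rather than cannot cover. It does not rescue the paragraph as written.

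A mixed model also uses partial data, so counting only completers is a worst case. That stands too.

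Three stronger readings are tempting and are not supported:

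- *The trial is underpowered for its primary aim.* On a single two-sided 5% test at 0.91, 46 per arm gives 99% power. The shortfall at .55 concerns a secondary outcome. The same section does expect moderate to large sleep effects, so 0.91 alone does not describe all the primary outcomes.
- *The inflation should have been 40/0.85, or 48 per arm.* That treats 15% as expected attrition. The plan describes 15% extra recruitment and expects drop-out to be minimal; 46 tolerates a 13% loss before falling below 40.
- *The recruitment figure conflicts with 92.* Participant recruitment says "For the RCT, 92 to 100 adolescents and their parent(s)/guardian(s) will participate in the study". Its lower bound is 92, so the two are compatible.

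**Conclusion.** The point holds as a failure of the stated justification. Two parts need little or no modelling: alpha is printed as .5, and a 15% increase cannot bridge a factor of 2.74 if 40 is truly the number for 0.91. The third part, 20 rather than 40 per arm at two-sided .05, assumes that β = 0.91 is a standardised mean difference. A total read as a per-condition figure would explain the 40, but the documents cannot confirm that.

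For d = .55, the two-sided .05 t-test puts power at 74% with no loss and 67% to 68% after an assumed 13% to 15% loss. It could reach about 80% or more under favourable assumptions that are not stated, and falls to 64% at 46 per arm under even a two-test correction.

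This should be fixed. It does not show that the trial is too small for its primary sleep effect at 0.91.

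**What to change.** Reword Sample size estimates and leave enrolment unchanged:

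1. Correct alpha to the value intended. State the number of tails, the effect metric and its scale (raw or change score), and the G*Power test with any correlation entered.
2. Say whether 40 is a total or a per-arm figure and which effect it belongs to, and correct it accordingly.
3. State what 46 per arm delivers. For example, at two-sided .05 before multiplicity correction: detectable d of about 0.59 with no loss and 0.64 with an assumed 15% loss; power for d = .55 of 74% and 67%. Give the corresponding figures at the multiplicity-corrected alpha alongside, since .05 will not be the per-test level once the correction in Statistical analysis is specified.
4. Delete the claim that the 15% add-on provides for the d = .55 ADHD outcome. Keep it as an allowance for drop-out and non-response, with the assumed rate stated.

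The cost is protocol wording only. No participants are added, but the stated power for the ADHD outcome becomes less favourable.

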#### **Data management**

Each participant will receive a unique code that allows to link the data of a participant over time, as well as to link all data of adolescents, parents, teachers and clinicians. After each assessment, the pseudonymized data are uploaded immediately from the researchers computers to secure network shared drives, whereas paper data is in locked archive cabinets. After all waves have been completed and all data has been linked, the dataset containing the names and codes is deleted. It is assured that data are stored securely. During the study, data is stored on secure network drives in the KU Leuven datacenter. The secure network drives are hosted by central ICTS services and managed by the IT service. More information on data management can be found in our Data Management Plan 'Blended CBT sleep intervention to improve sleep, ADHD symptoms and related problems in adolescents with ADHD - FWO DMP title' on <http://DMPonline.kuleuven.be> (this also includes further information regarding access to data and dissemination policy).

#### **Where is the treatment provided?**

The treatment will be provided within the KU Leuven Association at different locations (e.g. ADHD-clinic of the KU Leuven Academic Hospital, PraxisP, FARESA – Hasselt, FARESA – Brussels, ZitStil – Antwerp, Konekt – Gent and Huis in de Stad – Roeselare). There are written agreements stating that psychologists from SIESTA provide the training at these locations. In case of a COVID-19 outbreak or if preferred, the treatment is provided online via Mynexuzhealth (or via the platform of PraxisP, backup Skype for Business).

Data are gathered by questionnaires, diagnostic interviews and actigraphs. Every data gathering can take place online. Informants are parent(s)/guardian(s), teachers and adolescents. Some of the questionnaires and interviews might have already been completed during a diagnostic trajectory at the ADHD clinic. Patient files are consulted to gather that information, but where data are lacking all questionnaires have to be completed.

For the screening, all informants will fill out the questionnaires in Qualtrics and the researchers will be available either in person or via phone in case any questions arise. Additionally, the sleepinterview and K-SADS can be administered face-to-face or via Mynexuzhealth (or via the platform of PraxisP, backup Skype for Business). For pretest, posttest and follow-up, all questionnaires will again be filled out via Qualtrics. The questionnaires for the teachers will be send as a Qualtrics link via e-mail by the parent(s)/guardian(s), ensuring anonymity for the teacher towards the researchers.

The interviews are carried out and scored by researchers who were trained to use these instruments and in this methodology. Completion of all the applicable questionnaires takes an individual participant, parent/guardian or teacher maximum one hour at each time point.

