
When the adolescent meets inclusion criteria, the adolescent has to fill out the pretest questionnaires in Qualtrics. Parent(s)/guardian(s) of the adolescent are also asked to answer questionnaires in Qualtrics; also, they are asked to mail the link of the questionnaire (CPS) in Qualtrics to the teachers of the adolescent for their evaluation of the adolescent. Moreover the teacher will be asked how many lesson times per week he/she has contact with the participant. The names of the teachers will not be known by the researchers.

After the pretest is conducted, appointments for the treatment are made. However, participants are informed that those appointments can either happen as planned or that the treatment will take place 6 months later, due to the condition their child was assigned to. To avoid the possibility of a systematic bias in the assignment of participants to both groups (SIESTA treatment and treatment as usual (TAU) versus TAU only), randomization happens. We will use a stratified permuted block randomization based on medication use (yes/no) in blocks of 2 participants whereby an independent researcher performs the randomization. After the last treatment session, both the adolescent who followed the treatment and the paired adolescent from the TAU-group, are contacted by the researchers and provided with the actigraphs. The daily sleep logs are again filled out in Qualtrics. Within one week after the last treatment session a posttest session is planned in which the adolescent and parent(s)/guardian(s) are asked to fill out the questionnaires in Qualtrics. Filling out the questionnaires should not take longer than 1 hour for any informant. The actigraphs will again be picked up by a researcher or the courier service. The same procedure is applied during the follow-up measure after 3 months, including the actigraph/daily logs and the questionnaires. After follow-up, the treatment is provided to the adolescent in the TAU-group from that block.

In case of serious adverse events or a crisis situation, e.g. suicidality, during any phase of the study, (previously involved) clinicians will be contacted by the researchers. Also, if necessary at any time of the study, additional psychological aid can be given.

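### Nothing fixes or records which teacher completes the CPS at each assessment, and after randomisation the link reaches anonymous teachers only through parents who know the arm

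*Combined protocol and SAP*

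**What the plan says.** Secondary outcomes lists the CPS, completed by teachers, as a functional outcome. It is the only teacher-rated instrument named there.

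Where is the treatment provided? states that the teacher questionnaires "will be send as a Qualtrics link via e-mail by the parent(s)/guardian(s), ensuring anonymity for the teacher towards the researchers". Ethics & procedure describes the same route at pre-test: parents complete their own forms and "they are asked to mail the link of the questionnaire (CPS) in Qualtrics to the teachers of the adolescent". It adds that "The names of the teachers will not be known by the researchers". One item about the rater is collected: "Moreover the teacher will be asked how many lesson times per week he/she has contact with the participant". No use of that item in the analysis is stated.

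On timing, Where is the treatment provided? says "For pretest, posttest and follow-up, all questionnaires will again be filled out via Qualtrics", and it gives the burden for a teacher per time point. The post-test description in Ethics & procedure is narrower: "a posttest session is planned in which the adolescent and parent(s)/guardian(s) are asked to fill out the questionnaires in Qualtrics". The teacher is not mentioned there, and the follow-up is said to repeat that procedure.

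Ethics & procedure places the pre-test before families learn their condition. After that, Randomization and blinding says "neither participants nor clinicians can be blinded to allocation".

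Statistical analysis specifies a random intercept and slope per participant, with wave as a further level. Effect sizes are differences in change scores divided by the pooled SD of the changes. It has no term for the rater.

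**The concern.** A pupil in secondary education will usually have several teachers (assumed; the documents give no number). The plan does not say how many of them rate, who selects them, whether the same one rates each time, or how several ratings are combined. Teacher data are linked to the pupil's code (Data management), but no teacher code is described. From the data, a change of teacher therefore cannot be told apart from a change in the pupil.

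Two consequences follow, and they differ in kind. If teachers change for reasons unrelated to arm, CPS change carries between-teacher variance. That widens intervals and shrinks the plan's standardised effect, because its denominator is the SD of change. If the choice of teacher depends on arm after allocation, the between-arm comparison is biased, and no collected variable would reveal it.

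**Working it through.** The plan gives no figure for this effect, so there is nothing to reproduce. The textual check comes first, then an illustration on assumed inputs.

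**Text, by occasion**

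- *Pre-test:* the parent forwards the link before the condition is known. Arm-aware selection is not possible here.
- *Post-test and follow-up:* the parent knows the arm. The general statement on questionnaires implies a teacher rating, while the detailed procedure is silent on it. No rule or identifier ties these ratings to the pre-test teacher.
- *Analysis:* there is no rater term and no same-teacher sensitivity analysis.

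**Noise from change of teacher unrelated to arm**

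Inputs: CPS scaled to SD 1; same-teacher pre-post correlation 0.7 (0.6 to 0.8); different-teacher correlation 0.4 (0.3 to 0.5). All are assumed. The sample is 92, or 46 per arm (Sample size estimates).

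Formula: Var(change) = 2(1 − r). At central values this is 2 × 0.3 = 0.6 with the same teacher and 2 × 0.6 = 1.2 with a different one. If half switch, the average is (0.6 + 1.2)/2 = 0.9.

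| Same r / different r | Variance ratio, all switch | SE | Variance ratio, half switch | SE |
|---|---|---|---|---|
| 0.6 / 0.5 | 0.5/0.4 = 1.25 | +12% | 1.125 | +6% |
| 0.7 / 0.4 | 0.6/0.3 = 2.00 | +41% | 1.50 | +22% |
| 0.8 / 0.3 | 0.7/0.2 = 3.50 | +87% | 2.25 | +50% |

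At central values, 92 participants carry the information of 92/1.5 = 61 if half switch, and of 92/2 = 46 if all do.

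Power at central values, for an assumed true difference of 0.5 SD, 46 per arm and two-sided alpha 0.05, with SE = √Var × √(2/46):

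- No switching: √0.6 = 0.775, power 0.87.
- Half switch: √0.9 = 0.949, power 0.72.
- All switch: √1.2 = 1.095, power 0.59.

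The plan's standardised effect falls with it, from 0.5/0.775 = 0.65 to 0.5/0.949 = 0.53 and 0.5/1.095 = 0.46.

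**Bias, only if selection depends on arm**

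Bias = share of parents in one arm who steer × advantage of the chosen teacher. With a share of 0.5 and an advantage of 0.3 SD, it is 0.5 × 0.3 = 0.15 SD.

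For a range, let a steering parent pick the most favourable of k teachers. The advantage is then E(max of k) × √v, where v is the teacher share of score variance and E(max) is 0.564 for k = 2 and 1.163 for k = 5. The change variance is 0.6 + 2 × v × share.

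- Low end: share 0.1, k = 2, v = 0.1. Bias = 0.1 × 0.564 × √0.1 = 0.02 SD; type I error 0.051.
- High end: share 0.5, k = 5, v = 0.3. Bias = 0.5 × 1.163 × √0.3 = 0.32 SD; type I error 0.36.
- At a 10% share, the type I error is at most 0.066 over the same k and v.

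**The case against.** The strongest reply is that most of the alarming reading is inference. A reader might infer that parents who know the arm pick one teacher at every assessment. The documents do not say so: the pre-test precedes disclosure, and the link is to go to the pupil's teachers, in the plural, with no mention of selecting one. If several teachers answer each time, the open question is how their ratings are combined, and turnover of one of them matters less than the table shows.

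A reader might also infer that teacher differences are confounded with treatment. Ordinary turnover affects both arms and costs only precision. Ethics & procedure also says that one informant's answers are not passed to the others, so parents would have to guess who rates favourably. No motive or evidence for steering is given.

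Nor is the CPS the only check on unblinded family report. Actigraphy is an objective primary outcome for sleep. The CPS is the only named outside rating of school functioning.

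Finally, the magnitudes rest on assumed inputs, and the formula is for a two-point change, not for the three-occasion model.

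All of this stands, and it limits the point. It does not close the gap: the rater is neither fixed nor recorded, so a reader of the results could neither rule out selection nor estimate the noise.

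**Conclusion.** The point holds as a cheap improvement to one secondary outcome; no primary outcome is affected. Followed as written, the plan accepts an unknown loss of precision on CPS change and leaves any arm-dependent selection at post-test or follow-up undetectable.

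The loss is a 12% to 87% larger standard error if all pupils change teacher, and 22% at central values if half do, given the assumed correlations. The actual switching rate is unknown. Three of the five recruitment waves run January to March, so follow-up roughly six months later may fall in a new school year (calendar assumed), but equally in both arms. The bias figures of 0.02 to 0.32 SD show only what steering could do. The documents do not support a claim that it will happen.

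**What to change.** In Where is the treatment provided? and Ethics & procedure:

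- At pre-test, before randomisation, the parent designates the rating teacher(s) by school subject, without a name.
- The post-test and follow-up links are labelled for that subject.
- Each teacher form asks the subject and whether the respondent has rated this pupil before.
- The post-test and follow-up text names the teacher as an informant, so that the two sections agree, and says how ratings are combined if there is more than one.

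In Statistical analysis:

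- Keep all CPS ratings in the main intent-to-treat analysis. Restricting it to the designated teacher would select on an event after randomisation.
- Report the proportion with the same rater, by arm and occasion.
- Add a same-teacher sensitivity analysis, read as supportive only.

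The cost is two extra items and a line in the e-mail. The sensitivity analysis will be smaller where the teacher has changed or does not respond. No name is collected, so teachers remain anonymous to the researchers. The parent still forwards the link, so steering becomes detectable rather than impossible.
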